Exploratory Analysis 2.2: Analyses will be the same as described above for IES and INI-AD applied to the subgroup of African Americans. To formally test whether effects are the same, we will add an interaction term to the model for race to evaluate whether African Americans experience similar distress as those in the study who are not African American.

Aim 3: To explore how amyloid imaging disclosure will impact preventative health behaviors, advance planning for health (e.g. long-term care insurance decisions) and well-being (e.g. stigma, quality of life and relationships).

Study Subjects: All Study Participants, contrasting D+ and D- participants. Additionally, we will compare the A+D+ subjects to the A-D+ subjects.

Outcomes: We will focus on outcomes at 6 months of follow up after disclosure.

Measures: We have several categories of behavior to examine.

- 1) Preventive Health Behaviors: diet, vitamin intake, physical exercise and mental exercise, medication changes
- 2) Advance Planning: long-term care insurance decisions, other insurance decisions, completion of advance directives
- 3) Well-being: stigma, quality of life and relationships, sharing of information

Aim 3 Hypotheses:

Preventive Health Behaviors:

D+ individuals will show equivalent probability of undertaking preventative health behavior changes as D- individuals.

A+D+ individuals will show a higher probability of undertaking more preventative health behavior changes than A-D+ individuals.

Advance Planning:

Advance planning will occur with a similarly low frequency in D+ and D- individuals.

Advance planning will occur more frequently for A+D+ individuals than A-D+ individuals.

Well-Being:

D+ individuals will report more sharing of information than D- individuals.

Sharing of information will not differ between A+D+ and A-D+ individuals.

D+ individuals will report more stigma compared to D- individuals. This effect will be modified by amyloid status. A+D+ individuals will report more worries about stigma than A-D+ individuals.

D+ individuals will report similar QOL compared to D- individuals. This effect will be modified by amyloid status. A+D+ individuals will report lower levels of quality of life than A-D+ individuals

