Aim 3 Analyses: While we will examine each measure individually, our primary analysis will focus on aggregate summary measures for: 1) any preventative health behavior changes made over 6 months since disclosure that the participant reports, and 2) any advanced planning measures taken over the 6 months since disclosure. Separate bivariate analyses will be conducted for each of these summary measures. For 1) and 2), we will contrast the D+ and D- groups using chi-square statistics. We will also contrast the summary measures in the disclosed group by those with elevated and not elevated brain amyloid. We will conduct multivariable logistic regression analyses to control for any variables that appear to be confounders. We will use follow-up analyses to elucidate factors driving significant main effects.

For 3) Well-being, we will examine group differences in each stigma, quality of life and relationships, sharing of information at 6 months post disclosure. We will examine mean differences between groups on two measures of stigma (AD concern since learning risk/amyloid & Social Impact Scale) and conduct outlier analyses to identify potential predictors of extreme responses. We will use ordinal logistic regression to examine differences in quality of life as measured by an estimate of the impact of risk estimate/PET. To examine relationships and result sharing, we will use two-stage models to examine (a) decisions to share with others and (b) levels of satisfaction with this sharing. Analyses of decisions to share information will include a participant's sharing of each a risk estimate and an amyloid test result. Binary outcomes will be examined using unadjusted proportions and adjusted odds ratios. Analyses of satisfaction will include rank ordered levels of satisfaction with decision to share, of sharing a risk estimate, and of sharing an amyloid result. We will contrast groups defined by disclosure and amyloid status.

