Adjusted models will control for measured factors unbalanced across study groups and baseline values will be assessed as predictors of Aim 3 outcomes. All Aim 3 analyses will be conducted in the full group and also in the subgroup of disclosed study participants. Prior to analysis we will check that all model assumptions are adequately met. If not, we will adjust the analysis plan accordingly. Since these are exploratory analyses, we will use an alpha level of 0.05 to assess statistical significance. We will report estimates and their respective 95% confidence intervals.

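### Aim 3 predicts equivalent or similar behaviour in D+ and D- but names only a test of difference for it, with no margin and no rule for reading a non-significant result

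*SAP*

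**What the plan says.** Under Aim 3 Hypotheses, the SAP makes four predictions of no difference:

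- Preventive behaviour, D+ against D-: "D+ individuals will show equivalent probability of undertaking preventative health behavior changes as D- individuals".
- Advance planning, D+ against D-: "Advance planning will occur with a similarly low frequency in D+ and D- individuals".
- Quality of life, D+ against D-: "D+ individuals will report similar QOL compared to D- individuals".
- Information sharing, elevated against not-elevated amyloid among the disclosed: "Sharing of information will not differ between A+D+ and A-D+ individuals".

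Under Aim 3 Analyses, the first two are reduced to summary measures (any behaviour change, any planning step over six months), and the test is given: "For 1) and 2), we will contrast the D+ and D- groups using chi-square statistics". Logistic regression follows where variables look like confounders. Quality of life goes to ordinal logistic regression. Sharing decisions go to unadjusted proportions and adjusted odds ratios within a two-stage model.

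The section closes by calling Aim 3 exploratory, adding that "we will use an alpha level of 0.05 to assess statistical significance", and promising estimates with 95% confidence intervals. Neither document gives an equivalence margin, an interval-inclusion rule, an expected rate or a power statement for Aim 3.

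**The concern.** A chi-square test asks whether the data are incompatible with no difference. If it does not reject, the groups may be alike or the study may have been too imprecise to separate them, and the p-value does not say which. A hypothesis of equivalence needs the reverse: evidence that any difference is smaller than some stated amount. For preventive behaviour and advance planning the hoped-for result is the null, the named test can only count against the null, and no amount is stated.

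The effect of disclosure on behaviour is one of the two questions with which the protocol's Background opens. If the result is non-significant, the SAP leaves open whether the report may call the arms equivalent, and a real effect of moderate size could sit behind that word.

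**Working it through.** **Inputs from the documents.** Protocol, Power Calculation: 370 enrolled, about 10% dropout. Protocol, Visit #3: 1:1 randomisation. SAP, Aim 3 Analyses: alpha 0.05, 95% intervals. Completers: 370 × 0.9 = 333, and 333 / 2 = 166.5, so n = 166 per arm.

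**Assumptions.** The documents give no rates and no margin for Aim 3. The rates and margins below are illustrations.

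**Step 1. The plan's own figure.** There is none for Aim 3. The protocol's power figure belongs to Aim 1: 50 per group, SD 2.2, difference 1.25 PACC units, 80% power. A two-sided two-sample t-test at 0.05 gives 80.3%, so it reproduces, but it has no bearing on Aim 3.

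**Step 2. How often a real difference would be non-significant.** Power = Φ[(d − 1.96·SE0)/SE1], with SE0 = √(2p̄(1−p̄)/n) and SE1 = √{[p1(1−p1) + p2(1−p2)]/n}. For 10% vs 20%: (0.10 − 1.96 × 0.0392)/0.0388 = 0.597, and Φ(0.597) = 0.725.

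| True rates (assumed) | SE0 | SE1 | Power | Non-significant |
|---|---|---|---|---|
| 10% vs 20% | 0.0392 | 0.0388 | 72.5% | 27.5% |
| 20% vs 30% | 0.0475 | 0.0472 | 55.8% | 44.2% |
| 30% vs 40% | 0.0524 | 0.0521 | 48.0% | 52.0% |
| 50% vs 60% | 0.0546 | 0.0543 | 44.9% | 55.1% |
| 5% vs 10% | 0.0289 | 0.0288 | 40.8% | 59.2% |

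Using SE1 in place of SE0 moves the first row to 26.9%; hence about 27%.

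**Step 3. Precision of the planned interval.** The 95% half-width is 1.96·√(2p(1−p)/n).

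- Rate 10%: 1.96 × 0.0329 = 0.065, or 6.5 points.
- Rate 30%: 1.96 × 0.0503 = 0.099, or 9.9 points.
- Rate 50%: 1.96 × 0.0549 = 0.108, or 10.8 points.

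The sharing contrast lies within the disclosed arm and is smaller. With the target of 50 A+D+ and 166 − 50 = 116 A-D+, the half-width at 50% is 1.96·√(0.25 × (1/50 + 1/116)) = 0.166, or about 17 points.

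**Step 4. Could these numbers support equivalence under a proper rule?** Two one-sided tests at 0.05 are the same as requiring the 90% interval to lie inside ±m. With no true difference, power = 2Φ(m/SE − 1.645) − 1, where SE = √(2p(1−p)/n).

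| Rate (assumed) | m = 10 points | m = 15 points |
|---|---|---|
| 5% | 99% | about 100% |
| 10% | 84% | 99.6% |
| 20% | 47% | 92% |
| 30% | 27% | 82% |
| 50% | 14% | 72% |

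**Step 5. Why the margin must suit the rate.** Take a true 5% vs 10% and m = 10 points. SE = √[(0.05 × 0.95 + 0.10 × 0.90)/166] = 0.0288. The 90% interval falls inside the margin when the observed difference is below 0.10 − 1.645 × 0.0288 = 0.0527. That has probability Φ[(0.0527 − 0.05)/0.0288] = Φ(0.09) = 0.54. A doubling of a rare behaviour would be declared equivalent about 54% of the time.

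**The case against.** The best reply is that Aim 3 is exploratory in both documents, carries no power claim, and already promises 95% confidence intervals. Elsewhere the sponsor treats non-significance sensibly. In the SAP's contingency plan for Aim 1, a non-significant difference sends the analyst to the interval. The protocol's Data Analysis section says of exploratory hypotheses 1.2 and 2.3 that point estimates and intervals will be considered as well as p-values. On this view the four predictions are expectations, and a formal margin for self-reported summary measures is more than the aim needs.

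Much of this stands. It lowers the weight of the point and rules out several stronger readings that a reader might infer:

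- *That p>0.05 will be reported as equivalence.* The SAP nowhere says so; it is silent on how a non-significant result will be interpreted.
- *That p>0.05 is the plan's only route to supporting these hypotheses.* The planned intervals are another, although no rule is attached to them.
- *That the trial's data cannot show equivalence.* A non-significant chi-square cannot, but the data might: with a 15-point margin, 166 per arm gives at least 72% power at the rates in Step 4.
- *That chi-square is applied to all four hypotheses.* It is named for two; quality of life and sharing use other models.
- *That a real 10-point difference would usually be missed.* That depends on the rate: 27% of the time at 10% vs 20%, 55% at 50% vs 60%.

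The reply does not remove the mismatch itself. Exploratory status does not turn failure to reject into evidence for the null. The interval instructions for Aim 1 and for hypotheses 1.2 and 2.3 do not govern Aim 3. An interval without a margin shows what remains possible but does not say when the groups may be called equivalent.

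**Conclusion.** The point holds for the two D+ against D- behaviour hypotheses: the named test cannot support what is hypothesised, and no margin or reading rule fills the gap. The quality-of-life and sharing hypotheses lack a margin in the same way, under different models.

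Under the assumed 166 per arm and rates of 10% to 60%, a true 10-point difference would be non-significant in about 27% to 55% of trials, with a 95% half-width of about 6.5 points at a 10% rate and 11 points at 50%. These figures rest on assumed rates, and the documents do not say that 10 points is a difference that matters.

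This is a cheap improvement to an exploratory aim. It does not touch the primary analysis.

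**What to change.** In Aim 3 Analyses:

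1. For each of the four no-difference hypotheses, base the conclusion on the confidence interval for the group difference: the risk difference for binary measures, and the scale of the chosen model for the others.
2. State that p>0.05 will not be read as equivalence or similarity.
3. Use the word equivalent only if the 90% interval lies wholly inside a margin written down before analysis and scaled to the expected rate. Step 5 shows why one 10-point margin should not be applied to a rare outcome such as advance planning.
4. Where no margin can be agreed, reword the hypothesis as estimation of the difference with its interval.
5. Keep chi-square for the hypotheses that predict a difference.

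The cost is SAP wording and agreement on margins; no new data are needed. The downside is that some results which might have been called equivalent become inconclusive.

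### SAP Aim 3 predicts that amyloid status modifies the effect of disclosure on stigma and quality of life, but specifies no disclosure-by-amyloid interaction to test it

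*SAP*

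**What the plan says.** SAP Aim 3 Hypotheses, Well-Being, predicts more stigma in D+ than in D- and continues: "This effect will be modified by amyloid status. A+D+ individuals will report more worries about stigma than A-D+ individuals". For quality of life it predicts similar levels in D+ and D-, again states that amyloid status modifies the effect, and adds that "A+D+ individuals will report lower levels of quality of life than A-D+ individuals".

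The Study Subjects line of Aim 3 names the contrasts: "All Study Participants, contrasting D+ and D- participants. Additionally, we will compare the A+D+ subjects to the A-D+ subjects". Under Aim 3 Analyses the method for stigma is "We will examine mean differences between groups on two measures of stigma", and for quality of life "We will use ordinal logistic regression to examine differences in quality of life as measured by an estimate of the impact of risk estimate/PET". The well-being paragraph closes with "We will contrast groups defined by disclosure and amyloid status", without saying which groups are set against which. The final paragraph adds "All Aim 3 analyses will be conducted in the full group and also in the subgroup of disclosed study participants". It also plans to adjust for measured factors that are out of balance and to assess baseline values as predictors, sets alpha at 0.05 with 95% confidence intervals, and calls the analyses exploratory.

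No disclosure-by-amyloid term is written for any Aim 3 outcome. Elsewhere the SAP does write interaction terms: Exploratory Analyses 1.3 and 2.2 each add one for race in order to test formally whether an effect differs between groups.

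**The concern.** To say that amyloid status modifies the effect of disclosure is to say that the D+ minus D- difference is not the same in A+ as in A-. Neither named contrast measures that. Pooled D+ vs D- averages the two subgroup effects. A+D+ vs A-D+ compares two kinds of people within one arm.

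Disclosure is randomised; amyloid status is not. Protocol section III says that age and APOE ε4 are robustly associated with amyloid positivity. Participants in the D- arm also receive a dementia risk estimate that depends partly on age, so A+ and A- participants may differ in what they are told, and in how they react, even when no scan result is given. Analysis 2.1 pools the D- group only if A+D- and A-D- behave alike. Aim 3 has no such check.

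At stake is the reading of the well-being results. A difference between A+D+ and A-D+ could be taken as evidence that disclosure acts differently in A+ people when it partly or wholly reflects who is amyloid positive. A pre-existing difference of the opposite sign could equally hide real modification.

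**Working it through.** **The plan's own figure.** Aim 3 has no sample size or power statement, so the Aim 1 figure is used only to fix group sizes. The protocol's Power Calculation gives 50 per A+ group, SD 2.2, a difference of 1.25 and 80% power. With a two-sided alpha of 0.05, the t-test power at n = 50 is 80.3% for 1.25, and the difference detectable at 80% power is 1.245, which agrees with the SAP's 1.2451. The figure reproduces.

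**Inputs.**
- 370 enrolled, about 10% dropout and 100 A+ completers (protocol, Power Calculation): 370 × 0.9 = 333 completers, so 100 A+ and 233 A-.
- 1:1 allocation (protocol, Step 7): 50 A+ and 116.5 A- per arm.
- Alternative: 25% A+, the low end of the range in the SAP's Analysis 1.1, gives about 41.6 A+ and 124.9 A- per arm.
- Assumed: two-sided alpha 0.05 (Aim 3 does not state sidedness), equal SD in all groups, normal approximation.
- Assumed: an A+ vs A- difference without disclosure, b, of 0 to 0.5 SD. The documents give no value.

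**Identity.**

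Interaction = (A+D+ − A+D-) − (A-D+ − A-D-)

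A+D+ − A-D+ = interaction + (A+D- − A-D-) = interaction + b

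The pooled contrast weights the A+ and A- effects by about 100/333 = 0.30 and 0.70. It says nothing about how they differ.

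**Standard errors, in SD units.**

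- Within-arm contrast: √(1/50 + 1/116.5) = 0.169
- Interaction: √(2/50 + 2/116.5) = 0.239
- At 25% A+: 0.179 and 0.253

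**How often A+D+ vs A-D+ is significant when there is no modification.** The probability is Φ(b/0.169 − 1.96) + Φ(−b/0.169 − 1.96).

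| Assumed b (SD) | A+D+ vs A-D+ significant | Interaction test significant |
|---|---|---|
| 0 | 5% | 5% |
| 0.1 | 9% | 5% |
| 0.2 | 22% | 5% |
| 0.3 | 43% | 5% |
| 0.5 | 84% | 5% |

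At 25% A+ the entries for 0.2 and 0.3 SD are 20% and 39%.

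**What the interaction test can detect.** At 80% power: (1.96 + 0.84) × 0.239 = 0.67 SD, or 0.71 SD at 25% A+. Power for true interactions of 0.4, 0.5 and 0.6 SD is 39%, 55% and 71%. The 95% CI half-width is 1.96 × 0.239 = 0.47 SD.

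Quality of life is analysed by ordinal logistic regression, so the SD-unit figures are only illustrative for that outcome.

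**The case against.** The best defence is that the SAP offers more than the within-arm comparison. It contrasts D+ with D- in all participants, runs every Aim 3 analysis in the full group, and says it will contrast groups defined by both factors, which could include A+D- and A-D-. A reader might infer that A+D+ vs A-D+ is the only comparison planned; the text does not support that. It also never calls this contrast the test of modification, which could be read as a separate directional prediction. All this stands. But the four-group sentence names no contrast, and its place after the text on satisfaction with sharing leaves its reach unclear. The modification statements still have no test.

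Confounding is also partly handled. Measured imbalances are to be adjusted for, and age and APOE genotype are both measured. D- participants do not learn their amyloid status until after the 6-month outcomes, and one stigma measure and the quality-of-life measure are anchored to what was disclosed. The difference without disclosure may therefore be small. If it is zero, A+D+ vs A-D+ and the interaction estimate the same quantity and the planned contrast is the more precise. That is a fair limit on the size of the problem. Adjustment, however, reaches only measured factors and does not turn a within-arm comparison into an interaction.

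A reader might also infer that the planned contrast overstates precision, because its standard error is smaller by a factor of 1.41. It does not: 0.169 SD is correct for what that contrast estimates, and the ratio compares two different quantities.

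Lastly, Aim 3 is exploratory, its primary analysis rests on the health-behaviour and advance-planning summaries, and the interaction test will often be inconclusive. This lowers the priority but does not remove the mismatch between hypothesis and analysis.

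**Conclusion.** The point holds as a gap between a stated hypothesis and its analysis. For stigma and quality of life the SAP asserts modification by amyloid status and specifies no test of it, although it writes out interaction tests for race. The contrasts it names cannot answer the question unless A+ and A- participants would have the same outcomes without disclosure, and Aim 3 plans no named check of that.

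The size of the error depends on that unknown difference. Under the stated assumptions, the false-positive rate for a claim of modification drawn from A+D+ vs A-D+ runs from the nominal 5% (no difference) through 9% (0.1 SD) to 43% (0.3 SD). The documents do not show that a difference of any particular size exists, so none of these can be called the expected rate.

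No primary or safety conclusion is affected. The change is worth making but of lower priority.

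**What to change.** Add to SAP Aim 3 Analyses, for stigma (linear model) and quality of life (ordinal logistic model):

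- Fit disclosure, amyloid status and disclosure × amyloid in all four groups, with any planned covariates in the same model.
- Base any statement that amyloid status modifies the effect on the interaction estimate and its 95% CI.
- Report the randomised disclosure effect (D+ vs D-) separately within A+ and within A-.
- Keep A+D+ vs A-D+ as a descriptive comparison.
- Say which contrasts the sentence on groups defined by disclosure and amyloid status covers, and for which outcomes.

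The cost is a few lines of text and one model term per outcome. No extra data are needed, because all four groups are followed to 6 months. The downside should be stated in the plan: with a standard error of about 0.24 SD, and about 0.67 SD detectable at 80% power, a non-significant interaction is not evidence that modification is absent.

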Eligible participants will be cognitively and neuropsychiatrically normal, fluent English speakers, between the ages of 65-80, who have at least one first-degree relative with AD, are willing to undergo blinded (undisclosed) *APOE* genotyping, and are willing to participate in the randomized trial of amyloid imaging disclosure. Participants will be excluded if they have suffered a stroke or head trauma, have active medical or psychiatric illness that is unstable or progressive, or are taking acetylcholinesterase inhibitors or memantine. Participants with a history of anxiety or depression that has resolved or that has been treated and is stable will be enrolled. Formal documentation of AD family history will not be required as our previous REVEAL studies have demonstrated the reliability of self-reported family history of AD.

The inclusion and exclusion criteria for this study include assessment of participants' mood, especially symptoms of depression and anxiety, and persons who score above cut-off scores will be excluded. In addition, measures of depression and anxiety are endpoints of the study as well as measures of safety. We will decide participants' eligibility based on conversations between the study staff (clinician judgment) and participant, as well as pre-specified cut-off scores in screening measures to identify persons in need of additional monitoring:

- Geriatric Depression Scale (GDS) (range 0 to 15): > 10 exclude. 6-10 additional monitoring/use discretion on whether to enroll

- State-Trait Anxiety Inventory (STAI) (range 6-24): ≥ 19 exclude. 17-18 increased monitoring.

- Columbia Suicide Severity Rating Scale (CSSRS): Exclude any serious suicidal risk (investigator judgment)

To have a sufficient number of elevated amyloid participants for the planned analyses, we will enrich the participant pool with additional AD dementia risk factors. Age and having the *APOE* $\epsilon 4$ genotype are robustly associated with amyloid positivity and approximately 24% of unselected individuals will be $\epsilon 4+$. Our experience in the REVEAL Study has indicated that among persons who self-identify as having a first-degree family member with AD, the percentage of individuals who are $\epsilon 4+$ increases to about 47%. Thus, we will restrict participation to those who have such a family history.

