We will include all ethnic groups and men and women equally as part of this study. The study population will include both male and female healthy participants, 65 to 80 years of age. There is an increased ratio of women to men in AD, and it is anticipated that our recruited sample will reflect this ratio. Since AD affects individuals from all ethnic and racial backgrounds, every effort will be made to ensure a representative sample of preclinical AD participants. African Americans are historically underrepresented in clinical trials, including AD clinical trials. For this study of amyloid imaging disclosure, we will aim to recruit at least 25% African Americans through a partnership with Duke University. We expect that half of the participants at the Duke site will be African Americans.

IV. Subject Enrollment

All individuals who contact our study coordinator will be given a brief overview of the study, including all potential risks and discomforts, and will be asked if they would like to participate. At this initial contact, they will be given the opportunity to ask any questions and to consider whether they wish to participate. They will be informed that refusal to participate will not interfere with their future medical care. Whenever possible, the consent form will be given to them or mailed to the potential participant and study partner prior to the screening visit to allow the participant and study partner, as well as their family, to review the consent form in the privacy of their own home.

Should the participant be interested in participating, the study coordinator will set up a time to complete a phone interview (Phone Call #1). During the phone interview, subjects will provide verbal consent by expressing their interest in participating in the study. The phone interview will also explain that our participants will be randomized to one of two groups (initial disclosure of amyloid status; or delayed disclosure of amyloid status) and both groups will receive education and risk information for developing Alzheimer's disease dementia by age 85 based on age, gender, race, and family history of Alzheimer's disease dementia.

At the beginning of the participant's first in-person appointment (Visit #1), he/she will undergo an informed consent process and the consent form will be reviewed and signed by each participant and the study coordinator.

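### Aim 3, behaviour change and advance planning: the randomised A+D+ vs A+D- comparison is not specified, so the expected pattern of results could not be attributed to learning an elevated result

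*SAP*

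**What the plan says.** The Study Subjects line of SAP Aim 3 names two comparisons: "All Study Participants, contrasting D+ and D- participants. Additionally, we will compare the A+D+ subjects to the A-D+ subjects".

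The Aim 3 Analyses section says that "our primary analysis will focus on aggregate summary measures" for any preventive behaviour change and any advance planning over the 6 months after disclosure. Two contrasts follow. The first is "For 1) and 2), we will contrast the D+ and D- groups using chi-square statistics". The second is "We will also contrast the summary measures in the disclosed group by those with elevated and not elevated brain amyloid". Multivariable logistic regression will handle apparent confounders. On analysis sets: "All Aim 3 analyses will be conducted in the full group and also in the subgroup of disclosed study participants". The section describes the analyses as exploratory, sets alpha at 0.05 and promises 95% confidence intervals.

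The Aim 3 Hypotheses predict no D+ vs D- difference in behaviour change and similarly infrequent planning in both arms. They also predict more of both in A+D+ than in A-D+.

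Two Protocol passages bear on the second contrast. In section III, age and the APOE ε4 genotype "are robustly associated with amyloid positivity". In section IV, "both groups will receive education and risk information for developing Alzheimer's disease dementia by age 85", with age, gender, race and family history as the basis.

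**The concern.** The hypotheses that concern an elevated result are tested by comparing people who were told they are A+ with people who were told they are A-. Randomisation did not create those two groups. They differ in amyloid status and its correlates (age, APOE), and through age they can differ in the risk figure given to everyone at Visit 4. Within the disclosed arm every A+ person has been told, so being A+ and learning it coincide completely. No covariate set can pull them apart.

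Suppose the SAP's predicted pattern appears. At least three explanations fit it:

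- an elevated result prompts action, and pooling with the 70-75% who are A- dilutes the effect;
- an elevated result raises action and a not-elevated result lowers it, so the two offset in the pooled contrast;
- disclosure changes nothing, and A+ people act more anyway.

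The two planned contrasts cannot distinguish these. The A+D- and A-D- participants can, and the trial follows both groups to 6 months.

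**Working it through.** **1. Is the A+ pair specified elsewhere for these two measures?** Four passages come close.

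- The SAP sentence on contrasting groups by disclosure and amyloid status closes the well-being paragraph. It names no A+ pair.
- The SAP's follow-up analyses are tied to significant main effects, and the SAP predicts no D+ vs D- effect.
- Effect modification by amyloid status is stated only for stigma and quality of life.
- Protocol section VI says in general terms that other measures will be analysed like the primary outcome. That does not specify a contrast.

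So the pair is not specified for behaviour change or advance planning. The same Protocol section defends A+D+ vs A+D- in Aim 1 because it compares randomised groups within a pre-specified subgroup.

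**2. The plan's own figure for that pair (Aim 1).** Inputs: SD 2.2, two-sided alpha 0.05, 80% power.

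n = 2(1.960 + 0.842)² × 2.2² / δ². This gives 49 per group at δ = 1.25 (Protocol) and 50 at δ = 1.2451 (SAP). The plan's 50 per group reproduces. No power is stated for Aim 3.

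**3. Numbers available.** The Protocol gives 370 enrolled, about 10% dropout and 1:1 allocation. The A+ share is about 30% in the Protocol and 25-30% in the SAP.

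- Completers: 370 × 0.9 = 333.
- At 30% A+: 333 × 0.30 / 2 ≈ 50 A+ and 117 A- per arm.
- At 25% A+: 333 × 0.25 / 2 ≈ 42 A+ and 125 A- per arm.

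**4. Power.** The documents give no Aim 3 event rates. Assume 20% without an effect and 40% in A+D+, with no effect in A-.

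Power ≈ Φ[(|p1 − p2| − 1.96·s0) / s1], where s0 = √[p̄(1 − p̄)(1/n1 + 1/n2)] and s1 = √[p1(1 − p1)/n1 + p2(1 − p2)/n2].

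- *Pooled D+ vs D-, 167 per arm.* At 50/117 the D+ rate is (50 × 0.40 + 117 × 0.20)/167 = 0.260. The difference is 6 points and power = Φ[(0.060 − 0.090)/0.046] ≈ 25%. At 42/125 the difference is 5 points and power about 19-20%.
- *A+D+ vs A+D-.* At 50 vs 50, power = Φ[(0.200 − 0.180)/0.089] ≈ 59%. At 42 vs 42 it is about 52%.
- *A+D+ vs A-D+.* At 50 vs 117, power = Φ[(0.200 − 0.145)/0.079] ≈ 76%. At 42 vs 125 it is about 72%.

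Taking the formula together with simulated and exact binomial calculations, the ranges are 19-26%, 52-60% and 72-77%.

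**5. Cancellation.** At 30% A+, a rise of 20 points in A+ and a fall of 8.6 points in A- give 0.30 × 20 − 0.70 × 8.6 ≈ 0 in the pooled contrast.

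**6. A+D+ vs A-D+ when disclosure does nothing.** The A- rate is assumed to be 20%, the test is unadjusted and the background A+ vs A- gap is assumed.

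| Background gap | Rejects at p < 0.05 |
|---|---|
| 2 points | 6-7% |
| 5 points | 11-12% |
| 10 points | 28-31% |

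**7. Precision of the A+ pair.** At 40% vs 20%, the 95% half-width is 1.96 × √[(0.24 + 0.16)/n], which is ±18 points at n = 50 and ±19 points at n = 42.

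**The case against.** The strongest reply is that Aim 3 asks about amyloid imaging disclosure in general, whereas Aims 1 and 2 refer to disclosure of elevated amyloid. For the general question D+ vs D- in all participants is the right randomised comparison, and a null is what the SAP predicts. This stands. A reader might infer that the pooled contrast is invalid, but the documents do not support that. It only fails to isolate an elevated result, which the SAP's own A+D+ hypotheses concern.

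A reader might also infer that the randomised A+ pair is unused throughout. It is the primary contrast of Aim 1, and the SAP's well-being wording could cover it for those outcomes. The gap is confined to the two summary measures.

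Third, the confounding should not be overdrawn. APOE is neither returned to participants nor part of the risk estimate. Entry is limited to ages 65-80 with an affected first-degree relative, and adjusted models are planned. No document supports a particular background gap, and the rejection rates above are for unadjusted tests. Adjustment may well reduce the bias from measured factors, but it cannot separate knowing from being A+.

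Finally, the A+ pair has less power than the planned A+D+ vs A-D+ contrast: 52-60% against 72-77%. If the effect were 20% to 30%, the pair would have only 19-21%. That is correct. The pair's merit is that its estimate is randomised, not that it is more sensitive.

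**Conclusion.** The point holds as a gap in two exploratory analyses. It is not an error in a stated figure, and the trial's primary conclusion is unaffected. For behaviour change and advance planning, the SAP offers a valid randomised contrast for the overall effect of disclosing and a non-randomised contrast for the elevated result. It specifies no randomised contrast for the elevated result. The predicted pattern would therefore leave open whether the elevated result caused it.

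The missing contrast follows from the text alone. The sizes rest on assumed event rates, an effect confined to A+ participants, and 42-50 A+ completers per arm. The claim that A+D+ vs A-D+ will often mislead cannot be made from the documents: the excess over 5% is small at a 2-point gap and large only if the gap is near 10 points.

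**What to change.** In SAP Aim 3, for both summary measures at 6 months:

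- add A+D+ vs A+D- (effect of learning an elevated result) and A-D+ vs A-D- (effect of learning a not-elevated result), each with a 95% confidence interval; alternatively, fit one logistic model with a disclosure-by-amyloid interaction and report both stratum-specific estimates;
- keep D+ vs D- and describe it as the effect of a disclosure policy;
- keep A+D+ vs A-D+ but label it non-randomised, adjusted for age, sex, race, family history and APOE.

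The cost is a few sentences and two extra exploratory contrasts per measure, on data the trial already collects. The A+ pair will be imprecise, so its estimate and interval should carry the interpretation, and a non-significant result should not be read as no effect.
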